The problems with the studies carried out up to the moment of carrying out this protocol, in relation to medical error and non-technical skills, are varied. In the pilot study by Müller et al.(27), in which no sample size was calculated, a training day in resource management in CRM crisis was compared, a course that includes some dimensions of non-technical skills: leadership, assertive communication, situational awareness versus conventional medical management training in two scenarios in simulation; hemorrhagic shock and simulation non-intubation non-oxygenation situation; In both groups, performance measured with a checklist of treatment actions and non-technical skills measured with the Non-Technical Skills Scale for ANTS anesthesiologists was improved; without differences between both arms. However, no inference can be made from the population since this study has not been completed so far.

In the Khoo and Collaborators essay(28)An educational intervention was conducted to fill gaps in medical knowledge and aid in decision-making with decision algorithms in outpatient institutions, that is, only one dimension of the HNT, in primary care institutions. The results are not applicable to medical crises since it was carried out in a different context and also the way of measuring the outcome, review of medical records, is aimed at detecting an adverse event, that is, the potential damage derived from the care of health and not medical error.

In the study by Khan et al.(3. 4), only two specific dimensions of non-technical skills are included: assertive communication and teamwork; it was not possible to determine an overall reduction in medical error but a reduction in the risk of medical error with potential harm, a relative risk of 0.69 (95% CI 0.53 to 0.91) and an absolute risk reduction of 2% (95 CI). % 1 to 4).

The most important study on the reduction of medical error in crisis is that of Arriaga and Collaborators.(33) in which the use of checklists reduced the omission of simulation treatment steps with an absolute risk reduction of 17 and relative risk of 0.28 (95% CI). 0.18 to 0.42). These checklists impact one dimension of the HNT: resource management.

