10 hour program; two hours on the teleeducation platform that includes a description of the checklists to be used, reflection exercises with a previous test and a test at the end of the contents of the platform focused on checklists; and 8 face-to-face hours in high-fidelity simulation divided into two four-hour days with a minimum of three days of difference between them, in which directed and structured reflection (structured debriefing) will be emphasized to the mental models that are related to the checklists. In crisis.

The training will be carried out with four random crises from the list of the pathologies described, two in each session, this in order to avoid cognitive continuity bias.

To achieve the correct use of the checklist in crisis, directed and structured reflection will be carried out so that the participants acquire the following behaviors

- Choosing the right list for the stage
- Assignment of a specific participant using the checklist
- Feedback to the work team on each action suggested in the checklist

For the present protocol, the checklists in Spanish of the Colombian Society of Anesthesiology SCARE that are freely available will be used during the development of simulation crises.(41).

Recording for measurement of outcomes:

The measurement of the outcomes described in section 18, will be carried out after completing the training, on a day different from the last simulation session. To guarantee the homogeneity of the treatment teams, each participant will be evaluated separately in a group of four people where three are resident doctors trained in non-technical skills and checklists blinded to the intervention, since they do not participate in the training sessions. , who will assume the roles of two nursing assistants and a circulator.

Three crises will be carried out at random, different from those used in training to avoid cognitive continuity bias and will be recorded in the same simulation center for all participants with a Logitech[®] brand HD camera reference Pro stream C922 using a Jabra brand microphone [®] reference Speak 510Ms.

For all cases after recording for outcome measurement:

As the intervention and control are about educational strategies of problem solving skills in medical crises, in simulated environments in students from the same year of training, from

a single center, in which it is not possible to blind the participant, there may be communication between treatment and control groups.

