As the teaching-learning relationship is bidirectional, other educational interventions on technical skills related to the scenarios and the resolution of questions and doubts about the technical concepts related to the platform will be allowed for both groups.

No training will be conducted in either group on non-technical skills other than those contained in the training in this protocol.

12. Outcomes

12.1 Primary outcome:

Difference of proportions of omission of steps to treatment by group, the measurement of this outcome will be made by reviewing the recordings of three random medical crises different from those used for training in each group of participants. The evaluation will be done by an independent collaborator blinded to the intervention group and previously trained in the detection of errors by one of the authors. Failure to apply the specific actions defined in each pathology, chosen by the authors according to Annex 1, will be considered as omission of the treatment step, this includes the maximum time determined for each action, the choice of appropriate medications with their respective doses, among others. Each evaluation is independent, each crisis will be evaluated in seven steps,

12.2 Secondary outcomes:

12.2a 1Difference of crisis resolution time averages in seconds between both groups, measured in the recording, taking as the beginning of the crisis the moment of calling the treatment team and the end when all the effective treatment of each crisis is completed, according to the treatment steps described in Annex 1. In the event that the treatment steps are not fully completed, the time will be measured until the end of the simulation.

12.2b Difference of time averages in detection and discrimination of the crisis in seconds between both groups, taking as the beginning of the crisis the moment of calling the treatment team and the end the moment of explicitly requesting the specific checklist for the crisis or verbalize the diagnosis of the code situation. If the specific list is not requested or the diagnosis is not verbalized, the time until the end of the simulation will be counted.

12.2c Mean difference between the global non-technical skills score measured with the Ottawa global scale based on video recording by an independent evaluator.

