The proportion of treatment steps and not the incidence of medical error is taken as the unit of analysis, the reason for this is the high incidence of medical error that can even manifest itself with more than one error due to crisis, therefore, if used the incidence of the event would decrease the sample size.

Based on the study by Arraiga et al., The proportion of missed treatment steps in the expected control group is 26% and we consider a further 10% reduction in the intervention group to be clinically important. A minimum of 10% additional reduction in omitting treatment steps is decided because it is the approximate effect size of the other dimensions of non-technical skills other than resource management, a dimension that includes the use of checklists. It also establishes power of 90% and alpha of 0.05.

The sample calculation is then carried out in the analysis unit omitting treatment steps according to the formula:

$$n = \frac{\left[Z_{*} * \sqrt{2p(1-p)} + Z_{p} * \sqrt{p_{1}(1-p_{1}) + p_{2}(1-p_{2})}\right]^{2}}{(p_{1}-p_{2})}$$

With the statistical program R version 4.0.0 epiR statistical package, with the following code:

> library (epiR)

> epi.propsize (treat = 0.16, control = 0.26, n = NA, power = 0.9, design = 1, sided.test = 2, conf.level = 0.95)

We found a sample size of 492 treatment actions per arm, which corresponds to 984 in total, and with an estimate of student losses of 20%, we found the total of 1,180 treatment actions; Since 21 treatment steps are evaluated in each team, we obtain a total of 56 final semester medical students, 28 in each arm.

15. Recruitment

In order to complete the calculated sample size, the following recruitment strategies will be carried out:

- Explanation of the project at least once per internship cohort with the whole group.
- Request for participation on day 1 of the anesthesiology rotation in boarding school and the care rotation of the critically ill patient.

Table 8. Monthly evaluation of the monitoring status

Recruitment month	one	2	3	4	5	6	7	8
Current current income								
Income to date								
Income goal to date								
Real less projected								
Success ratio								
Projected final income								
Final deficit or excess								

IV Methods: allocation of interventions

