The analysis of each variable is explained in Table 9, prior to the use of parametric tests, the necessary assumptions will be verified including probability distribution tests, independence of the data and equality of variances according to the case. For the ratio of proportions and mean differences of the groups, in case of non-compliance, non-parametric statistical inference will be made.

To compare the intervention arm: training with non-technical skills and checklists with the control group: training with checklists, the proportion of omission of treatment steps per group will be used as the primary outcome variable.

Alternate hypothesis: the difference in the proportion of omission of treatment steps between the control and intervention group is greater than 10%.

Null hypothesis: the difference in the proportion of omission of treatment steps between the control and intervention group is 10% or less.

Table 9 analysis plan by variable

Outcome	Outcome	Statistical	Estimator	Analysis
	measure	hypothesis		method
Primary outcome: Medical error	Ratioofomissionoftreatmentstepsto totalstepsgroup.	Ha: Pcontrol - P intervention> 10% HO: Pcontrol - Intervention = 10%	Difference in proportions (95% CI)	Chi square test
Overall score on non-technical skills scale	Average Interval per group between 1 to 45	He has: µintervention>µcontrol Ho: µintervention≤ µcontrol	Mean difference (95% Cl)	T Student test.
Ottawa Leadership on Scale	Average Interval per group between 1 and 7	He has: µintervention>µcontrol Ho: µintervention≤ µcontrol	Mean difference (95% CI)	T Student test.
Ottawa scale problem solving	AverageIntervalpergroupbetween 1 and 7	AverageIntervalper groupbetween1 and 7	Mean difference (95% CI)	T Student test.
Situational awareness on the Ottawa scale	AverageIntervalpergroupbetween 1 and 7	Hehas:µintervention>µcontrolHo:µintervention≤µcontrol	Mean difference (95% CI)	T Student test.
Utilization of Ottawa scale resources	Average Interval per group between 1 and 7	He has: µintervention>µcontrol Ho: µintervention≤ µcontrol	Mean difference (95% CI)	T Student test.
Ottawa Scale Communication	Average Interval per group between 1 and 7	He has: µintervention>µcontrol Ho: µintervention≤ µcontrol	Mean difference (95% CI)	T Student test.
Crisis resolution time	Average time in minutes per group	He has: µintervention< µcontrol Ho: µintervention≥ µcontrol	Mean difference (95% CI)	T Student test.

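### Unresolved and undetected crises are timed to the end of the simulation, but no end is fixed, so a failed run stopped early can score as faster than a completed one

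*Combined protocol and SAP*

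**What the plan says.** Section 12.2a starts the resolution clock when the team is called and stops it when all the Annex 1 treatment for that crisis is complete. For failures it adds: "In the event that the treatment steps are not fully completed, the time will be measured until the end of the simulation". Section 12.2b stops the detection clock when the student asks for the specific checklist or states the diagnosis aloud. If neither happens, "the time until the end of the simulation will be counted".

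Table 9 defines the resolution measure as "Average time in minutes per group" and compares the arms with Student's t-test. Section 20a moves to non-parametric inference if assumptions fail. (Section 12.2 works in seconds, while Table 9 and Annex 5 use minutes. The units should be aligned, but this does not affect the point.)

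The paragraph on recording for outcome measurement says "Three crises will be carried out at random, different from those used in training" and describes the team, camera and microphone. It gives no run length and no rule for who ends a scenario or when. The durations the plan does give concern other things: 30 to 60 minutes of debriefing, four-hour training days, and time limits on individual Annex 1 steps.

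Two further passages bear on the point. Section 12.1 says "each crisis will be evaluated in seven steps" and defines omission broadly: "this includes the maximum time determined for each action, the choice of appropriate medications with their respective doses". Section 20c assigns multiple imputation to censored or lost data.

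**The concern.** The failure rule gives a crisis that was not resolved a number that depends on when someone stopped the run. If a failed scenario is stopped before a comparable completed one would have finished, the failure receives the shorter time and counts as better performance. A rank test does not help, because the early-stopped failure also ranks as fast.

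The harm cannot be undone at the analysis stage, since a recording that stopped too early cannot be extended. How much this matters depends on how often crises go unresolved, which the plan's own omission rates allow one to estimate for 12.2a.

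Two smaller gaps sit beside it. Section 12.2a does not say whether a late or wrongly dosed step counts as completed, although 12.1 scores it as omitted. Section 20c could be read as a second rule for the same observations.

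**Working it through.** **The plan's own figure.** The plan gives no figure for unresolved crises, scenario length or resolution time, so there is nothing to reproduce.

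**Do the Annex 1 limits supply an end time?** Annex 1 lists 11 crises of 7 steps, 77 in all. By my count, 28 steps carry a time limit, 5 carry only a repeat interval, and 44 carry neither. (One malignant hyperthermia step has broken text and is counted as neither.) In unstable bradycardia and unanticipated difficult airway the only timed step is the one-minute call for help. A step limit says when a step becomes late, not when the scenario ends.

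**Inputs for the share of unresolved crises**
- Control omission per step, section 14: "proportion of missed treatment steps in the expected control group is 26"%.
- Intervention omission per step, section 14: 16%.
- Steps per crisis, section 12.1: 7.
- Crises per arm: 28 students × 3 = 84, before losses.
- Lower control rate, from the background summary of the checklist trial ("absolute risk reduction of 17 and relative risk of 0.28"): without checklists 0.17 / (1 − 0.28) = 0.236; with checklists 0.236 − 0.17 = 0.066.
- Assumed, not in the documents: within-crisis correlation of 0.20, and half of scored omissions still counting as completed for 12.2a.

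**Formulas.** With independent steps, P(unresolved) = 1 − (1 − p)^7. With correlation r, I use a beta-binomial: P(unresolved) = 1 − the product over j = 0 to 6 of (b + j)/(a + b + j), where a + b = (1 − r)/r = 4 at r = 0.20 and b = 4(1 − p).

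**At the planned 26% and 16%**

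| Assumption | Control | Intervention |
|---|---|---|
| Independent; every omission is a step not completed | 1 − 0.74^7 = 0.878 | 1 − 0.84^7 = 0.705 |
| Correlation 0.20 | 0.716 | 0.524 |
| Half of omissions completed (p = 0.13, 0.08), independent | 0.623 | 0.442 |
| Half completed and correlation 0.20 | 0.450 | 0.303 |

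Out of 84 planned crises per arm, the first row is about 74 and 59, and the last row about 38 and 25.

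**At the 6.6% control rate**
- Independent steps: 1 − 0.934^7 = 0.380, about 32 of 84.
- Correlation 0.20: 0.257.
- Half completed (p = 0.033) and correlation 0.20: 0.136.

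No intervention share is given at this rate, because the planned 10-point reduction is not possible from 6.6%.

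**What the stopping time does to the estimate (illustration only).** Take the 0.450 and 0.303 shares and assume that completed crises average 8 minutes in both arms. If every failed run stops at time T, the control-minus-intervention difference is (0.450 − 0.303) × (T − 8). For T = 5, 10 and 15 minutes this is −0.44, +0.29 and +1.03 minutes. Student behaviour is the same in all three cases. The documents give neither T nor the 8 minutes, so this shows only that size and sign depend on an unset quantity.

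**Detection time.** The documents give no rate of failed detection, so no share can be computed for 12.2b.

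**The case against.** The best defence is that the gap is narrow. Section 12.2 gives a start, an end and an explicit rule for failures, so only a run time is missing, and that could be regarded as scenario-script detail. A floor is also implied. Lateness against a step limit cannot be scored unless the recording runs past that limit, which in nine of the eleven crises implies a run beyond the call for help. Arms are randomised, the team residents and the outcome assessor are blinded, and all recordings use the same centre.

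Much of this stands. The implied floor makes very early stops less likely, and nothing shows that stopping would differ by arm. A reader might infer that the rule favours one arm; the documents do not support that. Nor is it a problem that crisis types may run for different lengths, since crises are drawn at random in both arms.

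The defence does not close the gap. The floor is unwritten and is not an end time. For arrest with ventricular tachycardia the latest limit is 3 minutes, although one step repeats every 3 to 5 minutes. For unstable ventricular tachycardia it is 5 minutes, with an untimed step after it. Blinded video scoring takes place after the stop, so it cannot standardise it.

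On 20c, the specific rule in 12.2 can reasonably be taken to prevail. That part is a wording ambiguity.

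**Conclusion.** The concern holds as a gap in the definition of two secondary outcomes: crisis resolution time, and time to detection and discrimination. The primary outcome does not use this rule.

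The share of control resolution times set by the stopping point lies between about 14% and 88%. It depends on the omission rate (6.6% or 26%), on within-crisis correlation, and on whether late or wrongly dosed steps count as completed. The 88% and 70% figures are upper values. They assume independent steps, that every scored omission is a step not completed, and that conditional steps always apply. A reader might infer from them that most resolution times are certain to be set by the stop; the lower end of the range does not support that. Nor can these shares be carried over to detection time.

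The conclusion rests on the available text. Some pages and the figures could not be seen, but the sections defining the outcomes and the recording are present, and neither points elsewhere for an end time.

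**What to change.** Make these changes before recording starts:

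- **Run time.** The authors set a maximum run time for each crisis type, or one common time, identical in both arms. It must be long enough for all seven steps, including untimed and repeated ones, and therefore longer than the latest Annex 1 limit for that crisis.
- **Stopping.** Run every scenario to that time, or stop early only by a scripted criterion applied identically in both arms.
- **Scoring failures.** Enter any crisis scored from video as unresolved or undetected at the maximum, whatever the actual stop. This also covers a live judgement of completion that the video scoring later contradicts. The planned mean difference then becomes a restricted mean difference with a known horizon.
- **Definition of completed.** State for 12.2a whether late steps, wrongly dosed steps, and conditional steps that were never triggered count as completed.
- **Reporting.** Give the proportions resolved and detected per arm beside the mean times.
- **Section 20c.** State that multiple imputation applies to missing sessions or recordings, not to these times.

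The cost is wording in the analysis plan and scenario scripts, and somewhat longer recording sessions because failed scenarios run to the limit.

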12.2d Mean difference between the discriminated score between dimensions of the nontechnical skills of the two groups, measured with the Ottawa global scale based on video recording by an independent evaluator.

Ottawa Global Scale Overview: this scale is free to use for research, it has a validation study in our environment, completed in the publication phase, its psychometric characteristics are summarized in Table 5 (42), the Spanish version can be seen in Annex 6.

Table 5 Ottawa scale psychometric characteristics for HNT

Dimension or item	Internal	Reliability between	Reliability between Reliability re-	
	consistency	ICC evaluators	test	
Overall evaluation	reference	0.641	0.761	
Leadership Skill	0.902	0.634	0.808	0,776
Problem resolution	0.915	0.628	0,779	0.692
Situational awareness	0.930	0.627	0.708	0.576
Use of resources	0.863	0.696	0.70	0.578
Communication skills	0.893	0.597	0.7407	0.872

12.2e Student satisfaction:

This exploratory outcome is chosen because of the importance of the perception of the participants that hypotheses could generate for future research. A search was made of validated and free scales for use without finding any that meets these requirements for high-fidelity simulation, therefore, the training satisfaction assessment format of the simulation center of the Faculty of Medicine of the University of Antioquia, format F-025-08 (see annex 7).

12.2f Incidence of inadequate crisis management:

Difference in incidence of inappropriate management rating, this dichotomous rating will be performed by the blind evaluator of the outcomes, taking into account the treatment actions considered minimal by the researchers based on the different clinical practice guidelines, these are those specific to management by crisis, it will be classified as adequate management if it is met, inadequate management otherwise, according to table 6.

Air embolism	 Stop the air intake site by applying irrigation Start dobutamine or norepinephrine if hypotension in less than 2 minutes Position in lateral decubitus on the affected side before 10 minutes
Anaphylaxis	 Stop infusions Apply Adrenaline IM or IV in less than 2 minutes Apply infusion epinephrine in case of non-response of 1 to 4 micrograms / minute
Unstable Bradycardia	 Apply atropine 0.5mg IV repeat up to 3mg total dose If bradycardia persists use transcutaneous pacemaker

Table 6. Minimum	treatment	actions for	crisis	resolution.
	cicacificiti		011515	resonation.

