Cardiac arrest / Asystole (hypoxemia)	 Start cardiac massage in less than a minute Apply 1mg adrenaline every 3 to 5 minutes Use of advanced airway device in less than 5 min
Cardiac Arrest / Ventricular Tachycardia	 Start cardiac massage in less than 1 minute Rhythm detection every 2 minutes Application of electric shock with 200J bipolar in less than 3 minutes
Unanticipated difficult airway	 Apply FiO2 100% Perform minimum 3 laryngoscopies maximum 4 Use second-generation supraglottic after laryngoscopy failure
Hypovolemic shock from open trauma	 Verify the patency of 2 peripheral veins Administer 20ml / kilo bolus of crystalloids in less than 5 minutes Request Mass Transfusion Package
Distributional shock hypotension	 Apply 20ml / kilo crystalloid bolus in the first 5 minutes Start norepinephrine at a dose of 0.05ug / k / min in less than 5 minutes
Malignant hyperthermia	 Apply Dantrolene at a dose of mg / kg in less than 5 minutes Suspend possible triggers of the crisis
Foreign body airway obstruction	 Apply FiO2 100% Apply support with positive pressure ventilation in less than 4 minutes Manual removal of foreign body in less than 5 minutes
Unstable ventricular tachycardia	 Cardiovert in synchronous mode with 100 Joules in the first 3 minutes Perform second cardioversion with 150 Joules in the first 5 minutes

13. Figure 2: Participants timeline

[figure not shown]

Table 7. Follow-up program and procedures

	Reclu	Assign					D	. +	211		tion	stage				Closir	20
Time in days					1	1	P	551-	alli	JLa	1	eleve	1	1	1	fiftee	ושי 1
Time in days	one	one	2	3	4	5	6	7	8	9	_		_	_	_		
Exercise																	
Assignment																	
Allocation screening																	
Theoretical knowledge test																	
Informed consent																	
Assignment																	
Intervention																	
Post-test virtual platform																	
HNT and LC training																	
LC training																	
Evaluations																	
Baseline measurement																	
Recording of outcome crisis																	
Outcome measurement																	
Measurement of secondary																	
outcomes																	

Reclu: Recruitment, Assig: Assignment.

14. Sample Size

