Timeindetectionanddiscrimination ofthe crisis	Average time in minutes per group	He has: µintervention< µcontrol Ho: µintervention≥ µcontrol	Mean difference (95% CI)	T Student test.
Student satisfaction	Difference of excellent assessment proportions in the categories of the format F- 025-08	Ha: Pintervencion> Pcontrol Ho: Pintervencion = Pcontrol	Difference of proportions. (95% CI)	Fisher's Exact Test.

IncidenceofRelativeriskHa: RR ≠ 1improperinadequateHo: RR = 1handlingmanagementintervention /control	Relative Risk (95% CI)	Chi square test.
--	---------------------------	------------------

20b. Additional analysis methods

Other analyzes by subgroups or adjustment of analysis by other variables will not be considered.

20c. Methods for analysis of censored or missing data

In case of censored or lost data, multiple imputation method will be carried out (43).

VI Methods: data monitoring

21a. Composition of the data monitoring committee

The Tecrisis study will have a data monitoring committee external to the research group, which will be made up of the coordinator of the simulation center of the Faculty of Medicine of the University of Antioquia, a clinical simulation teacher from outside the study, and a researcher from the research group. GRIMPA Research in Perioperative Medicine.

21b. Interim Analysis Description

An interim analysis will be carried out with 50% of the participants collected, blind and foreign to the research group, only for adverse events in the case suggested by the data monitoring committee.

22. Damage

Given that it is an educational study that uses the same strategies that are usually used in the training of participants, no adverse events are expected other than a possible emotional affectation due to the high fidelity simulation. The report and management of this will be done according to the institutional protocol of the simulation center of the Faculty of Medicine of the University of Antioquia. However, this study is low risk since the participants are constantly exposed to simulation as a teaching tool and reaching an adequate degree of stress can improve learning even in this scenario.

Other unforeseeable adverse events within this protocol will be reported in case of presenting to the simulation center of the Faculty of Medicine of the University of Antioquia and to the ethics committee of the same institution.

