Annex 5: Table of variables

Variable	Operational definition	Nature	Scale	Unit or code
X 1	Age	Continuous quantitative	Reason	Years
X 2	Sex	Qualitative	Nominal	1. woman, 2. man
Х З	Personal history of sleep disorders	Qualitative	Nominal	0. no, 1. yes
X 4	Personal history of mood disorders	Qualitative	Nominal	0. no, 1. yes
X 5	Hours of weekly care rotation	Continuous quantitative	Reason	Hours
X 6	Weekly working hours	Continuous quantitative	Reason	Hours
X 7	Hours of sleep the day before measurement outcome	Continuous quantitative	Reason	Hours
X 8	Average daily sleep hours	Continuous quantitative	Reason	Hours
X 9	Self-reported hours of simulation training	Continuous quantitative	Reason	Hours
X 10	Failure rate of treatment steps	Continuous quantitative	Reason	Percentage
X 11	Overall score on non-technical skills scale	Discrete quantitative	Interval	1 to 7
X 12	Ottawa Leadership on Scale	Discrete quantitative	Interval	1 to 7
X 13	Ottawa scale problem solving	Discrete quantitative	Interval	1 to 7

X 14	Situational awareness on the	Discrete	Interval	1 to 7
	Ottawa scale	quantitative		
X 15	Utilization of Ottawa scale	Discrete	Interval	1 to 7
	resources	quantitative		
X 16	Ottawa Scale Communication	Discrete	Interval	1 to 7
		quantitative		
X 17	Crisis resolution time	Continuous	Reason	minutes
X 18	Time in detection and	quantitative Continuous	Reason	Minutes
V 10	discrimination of the crisis	quantitative	Reason	winnutes
X 17	Inadequate crisis management	Qualitative	Nominal	0. no, 1. yes
	· · ·	atisfaction format		01110) 11 900
X 18	Mastery of course topics	Qualitative	Ordinal	0. Poor
V 10	Wastery of course topics	Quantative	Orumai	1. Acceptable
				2. good
				3. Excellent
X 19	Exhibition security	Qualitative	Ordinal	0. Poor
				1. Acceptable
				2. good
				3. Excellent
X 20	Clear and accurate answers to	Qualitative	Ordinal	0. Poor
	questions			1. Acceptable
				2. good 3. Excellent
X 21	Ability to arouse interest	Qualitative	Ordinal	0. Poor
~ = =	, to may to arouse interest	Quantative	oruna	1. Acceptable
				2. good
				3. Excellent
X 22	Efficiency in the use of class time	Qualitative	Ordinal	0. Poor
				1. Acceptable
				2. good
		a		3. Excellent
X 23	Order, coherence and clarity in the	Qualitative	Ordinal	0. Poor
	presentation of the topics			1. Acceptable 2. good
				3. Excellent
X 24	Punctuality and attendance at class	Qualitative	Ordinal	0. Poor
	sessions			1. Acceptable
				2. good
				3. Excellent

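### Inadequate crisis management (12.2f) has no stated unit of analysis or rule for combining three ratings per student, and 12.2f and Table 9 name different effect measures

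*Combined protocol and SAP*

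**What the plan says.** - **Recordings.** Section 11a, under the recording of outcomes: "Three crises will be carried out at random, different from those used in training". Each participant is assessed separately, so each contributes three recordings.
- **Rating.** Section 12.2f: "Difference in incidence of inappropriate management rating, this dichotomous rating will be performed by the blind evaluator of the outcomes". On the criteria: "these are those specific to management by crisis, it will be classified as adequate management if it is met, inadequate management otherwise, according to table". The table meant is Table 6, which gives a separate set of minimum actions for each of 11 crises. Seven crises have three actions and four have two.
- **Analysis.** The last row of Table 9 (section 20a) gives the estimator as "Relative Risk (95% CI", with a two-sided hypothesis about the relative risk and a chi-square test.
- **Data dictionary.** Annex 5 has one row: "Inadequate crisis management Qualitative Nominal 0. no, 1. yes". It carries no crisis index and no statement of the record level.
- **Size.** Section 14 gives 28 students per arm. It plans the primary outcome on step-omission rates of 26% (control) and 16% (intervention). It gives no expected rate, effect or power for inadequate management.

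**The concern.** A mean score or mean time over three crises has an obvious default. A yes/no rating does not. The text is compatible with counting every crisis, or with classing a student as inadequate after any one, at least two or all three crises rated inadequate. These are different outcomes, with different control incidences and different effects.

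The choice also decides whether the stated test is valid. If crises are counted, three ratings from one student enter the chi-square as if they came from three people. If students are counted, the test is valid, but information is discarded and the answer depends on a rule that nobody has written down. Section 17a says that those analysing the data will not be blinded (section 19 says the data reach the analyst blinded), so the rule should not be left until analysis.

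The conflict between a difference in 12.2f and a relative risk in Table 9 is a separate defect: it leaves open which figure is the main result.

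**Working it through.** The plan gives no figure for this outcome, so there is none to reproduce. The checks below show what the open choices would do.

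**1. Units.** 28 students × 3 crises = 84 ratings per arm at full enrolment, against 28 student results per arm.

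**2. Plain chi-square on 84 ratings per arm.** With three ratings per student and within-student correlation ρ (within arm), the variance is inflated by 1 + (3 − 1)ρ = 1 + 2ρ. The true two-sided error at nominal 5% is 2[1 − Φ(1.96/√(1 + 2ρ))]. The documents give no ρ, so 0.1 to 0.3 is assumed.

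- ρ = 0.1: √1.2 = 1.095; 1.96/1.095 = 1.789; error about 7%.
- ρ = 0.3: √1.6 = 1.265; 1.96/1.265 = 1.549; error about 12%.

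**3. Collapse to one result per student.** Assumptions: section 14's 26% and 16% apply to the Table 6 actions; every listed action is required; omissions are independent within and between crises; all 11 crises are equally likely.

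Probability that a crisis is adequate, with q = 1 − omission rate: (7q³ + 4q²)/11.

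- Control, q = 0.74: (7 × 0.4052 + 4 × 0.5476)/11 = 0.457, so p = 0.543 inadequate.
- Intervention, q = 0.84: (7 × 0.5927 + 4 × 0.7056)/11 = 0.634, so p = 0.366 inadequate.

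| Rule | Formula | Control | Intervention | Relative risk | Difference (points) |
|---|---|---|---|---|---|
| Per crisis | p | 54.3% | 36.6% | 0.67 | −17.7 |
| Any of three | 1 − (1 − p)³ | 90.5% | 74.6% | 0.82 | −15.9 |
| At least two | 3p² − 2p³ | 56.4% | 30.4% | 0.54 | −26.1 |
| All three | p³ | 15.9% | 4.9% | 0.31 | −11.1 |

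The tabulated values come from averaging over every set of three different crises. The formulas applied to the mean p give the same relative risks to two decimals.

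**4. Sensitivity.** Letting a student's three ratings correlate (beta-binomial) leaves the per-crisis relative risk at 0.67 and pulls the others towards it:

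| Correlation | Any of three | At least two | All three |
|---|---|---|---|
| 0 | 0.82 | 0.54 | 0.31 |
| 0.1 | 0.81 | 0.57 | 0.38 |
| 0.3 | 0.78 | 0.62 | 0.48 |

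Crisis mix matters too. With only three-action crises, the any-of-three and at-least-two relative risks are 0.85 and 0.57; with only two-action crises, 0.78 and 0.49.

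**5. Difference against relative risk.** Both come from the same two incidences. Moving from one to the other changes what is reported; it does not change the relative risk.

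**The case against.** The best defence is that the text already points to a per-crisis count. The outcome's name, the criteria in 12.2f and the layout of Table 6 are all by crisis, the primary outcome is also counted below student level, and the any, most and all rules appear nowhere. This is fair, and it makes per crisis the likelier reading. But on that reading Table 9's chi-square is the wrong test, so the defence replaces one problem with another. Section 20a does promise to check independence and to use non-parametric inference if assumptions fail. The usual rank and exact tests also need independent observations, so that fallback does not deal with three ratings per student.

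A reader might infer from the single Annex 5 row that one yes/no per student will be stored. The documents do not say so. Annex 5 is a list of variables, and the two time outcomes also have one row each although they are timed within a crisis. The rating form is not reproduced.

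A reader might also infer that a collapse at data entry would be irreversible. Section 27 says that the outcome videos are stored with a backup, so the crises could be rated again.

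Finally, this is one of several secondary outcomes and has no sample-size target. That limits its weight but does not make its analysis defined.

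**Conclusion.** The point stands as a gap in definition with a consequence for validity. The unit and the combining rule are missing, and two effect measures are named. On the likelier per-crisis reading, the stated test has a type I error of about 7% to 12% instead of 5%, given an assumed within-student correlation of 0.1 to 0.3. On a per-student reading, the relative risk depends on the rule, and an any-of-three rule would put the control arm near a ceiling at about 90%.

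The relative risks of 0.82, 0.54 and 0.31 are illustrations under the assumptions listed in the working. They are neither bounds nor predictions, and correlation within students brings them closer together. It would be wrong to read the mismatch between difference and relative risk as a cause of that spread; it is a second, independent inconsistency.

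The primary outcome is not affected. The change should be made before outcome rating begins.

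**What to change.** - **Annex 5 and the rating form:** record the adequate/inadequate rating for each of the three crises, with the crisis identified.
- **12.2f and Table 9:** define one measure, the proportion of a student's three crises rated inadequate (0, 1/3, 2/3 or 1), with the student as the unit.
- **Test:** replace the chi-square with a student-level comparison of mean proportions, for example a t or permutation test with a 95% confidence interval. A per-crisis model with standard errors clustered by student serves the same purpose.
- **Effect measure:** name the same main measure in 12.2f and Table 9, and give the other as a supplement. A difference would match the primary outcome's scale, but either choice resolves the conflict.

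When every student has three ratings, the mean of the student proportions equals the per-crisis incidence, so the likelier reading of the outcome is kept and only its precision is corrected. The cost is at most two extra form fields, one reworded row of Table 9 and a sentence in 12.2f. The evaluator already judges each recording.
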